Bioven should be administered intravenously dropwise at the initial rate of 0.5-1.0 ml/kg of body weight/hour for 30 minutes. If no adverse reactions occur, the rate of administration may be gradually increased (it is recommended to increase by 0.5-1.5 ml/kg of body weight/hour every 10 min). According to the data from clinical studies the maximum rate of administration is 8.5 ml/kg of body weight/hour.

The study drug is administered only in hospital environment while observing the rules of aseptic. The solution should be of room temperature before use. Cloudy solutions and those containing sediment are not used. For the administration of the drug, it is necessary to use a separate infusion system.

When administering the drug, it is necessary to consider the information specified in the relevant sections of the instructions for medical use: administration details, special safety measures, contraindications, interaction with other medicinal products, etc.

Patients participating in this study may receive concomitant therapy, which is used for the treatment of comorbidities and life-threatening conditions.

It is allowed to use glucocorticoids in a stable dose for at least 2 weeks before starting treatment with the test drug. The need to increase the dose of corticosteroids during the study is considered as ineffective use of the study drug.

Duration of treatment:

The duration of treatment with the study drug for each patient is no less 2 days. The total period of stay in the study is 4 weeks.

Efficacy and safety endpoints: Efficacy:

Primary efficacy endpoint:

| Bioven | |
|----------------------------|--|
| Trial Code: 2021-BV-ITP-BP | |

Page 11 Version 1.4 from July 03, 2023,

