After the informed consent form is signed, the screening tests are performed and the compliance with the inclusion / non-inclusion criteria is evaluated. The patient who passed the screening tests is enrolled in the study.¹

Clinical phase

Patients enrolled in the study receive Bioven at a dose of:

0.8-1.0 g / kg intravenously once a day for 2 consecutive days, the course dose is 1.6-2.0 g / kg. Allowed repeat course at same dosage in period 14-28 days from first infusion, if required.

The CRF records the time of administration of the study drug, the occurrence of possible adverse events.

Prescribed therapy and diagnostic results are recorded in the CRF based on the primary documentation.

Data are entered into the CRF according to the patient management plan.

Follow-up phase and completion of the study

This stage lasts for 4 weeks after the last administration of the drug (possible repeat course is not considered).

In all patients, the platelet count will be determined 48 hours after the start of the first administration of the study drug, on the 7th (\pm 1 day), 14th (\pm 2 days), 21st (\pm 3 days), 28th (+ 1-3 days) days after the start of therapy.

The results of the study are evaluated by endpoints.

Phase-by-phase breakdown and breakdown of visits are detailed in Section 6.4 "Tabulated schedule of events". Information is entered into the CRF after each visit, according to the "Schedule of study events".

The decision on any examinations and diagnostic procedures in routine clinical practice is made and controlled by professionals.

Blood sampling for platelet count is performed 6 times:

- at the screening phase;
- 48 (\pm 3) hours after the start of study drug administration;
- on the 7th (± 1) day from the start of study drug administration;
- on the 14th (± 2) day from the start of study drug administration;
- on the 21st (± 3) day from the start of study drug administration;
- on the 28th (+ 1-3) day from the start of study drug administration.

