5th visit (Day +21 \pm 3 days) – physical examination, assessment of the status of hemorrhagic syndrome, blood sampling to determine platelet count, manual platelet counts, biochemical blood test, Coombs test in case hemolysis was detected during the previous visit (according to the laboratory data).

If a decrease of platelets count $< 30 \times 10^9/L$ was recorded, then approximately a day after the visit, an additional blood test is performed with a platelet count.

This visit can be performed by telephone / video, provided that the patient's status can be adequately assessed and biomaterials for laboratory tests can be sampled in Local Laboratory or at the collection point of the Central Laboratory designated by the Sponsor;

6th visit (Day +28 + 1-3 days) – physical examination, assessment of the status of the hemorrhagic syndrome, blood sampling to determine platelet count, manual platelet counts, biochemical blood test, Coombs test, Total IgG levels (g/l).

If a decrease of platelets count $< 30 \times 10^9/L$ was recorded, then approximately a day after the visit, an additional blood test is performed with a platelet count.

This is a face-to-face visit. Completion of the study.

Statistical analysis:

Populations for statistical analysis:

ITT (Intention-to-treat population) – all participants of the study who have taken the study drug at least once. The data obtained from this sample will be used for safety analysis.

PP (Per Protocol) – all patients who have met the requirements of the protocol. This population includes all patients who received the protocol-prescribed therapy in full, who completed all the prescribed visits and did not have significant deviations from the protocol. The data obtained from this sample will be used for analysis based on efficacy criteria.

Sample size calculation.

Statistical analysis of endpoints will be descriptive with testing of the null hypothesis (non-inferiority study).

In accordance with the EU recommendations on the clinical investigation of human normal immunoglobulin for intravenous administration (*Guideline on the clinical investigation of human normal immunoglobulin for intravenous administration (IVIg), EMA/CHMP/BPWP/94033/2007 rev. 4, 16 Dec 2021*) the obtained results will be compared with literature data.

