4.4 Stages of the study. Follow-up and completion of the study

The stage starts after the last administration of the drug and lasts for 4 weeks. At this stage a set of laboratory tests, measurement of vital signs is carried out. AE/AR registration is also performed. The results of the study are entered into the CRF according to the "Schedule of research procedures" (Section 6.4 Table 1 of the Protocol).

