6th visit (Day +30 \pm 3 days) - physical examination, assessment of the status of the hemorrhagic syndrome, blood sampling to determine platelet counting by the Fonio method, biochemical blood test, Coombs test, determination of Ig G levels (g / l). This is a face-to-face visit. Completion of the study.

Patients' serum samples should be stored frozen at the temperature of -65 - -85 $^{\circ}$ C (second aliquot) to ensure the possibility of performing repeat laboratory tests, if necessary, in the future.

Patients receive Biven 10% solution for infusion, produced by LLC "Biopharma Plasma" at a dose of 0.8-1.0 g / kg 1 time per day for 2 consecutive days, the course dose of 1.6-2.0 g / kg. Allowed repeat course at same dosage in period 14-28 days from first infusion, if required.

Bioven should be administered intravenously dropwise at the initial rate of 0.5-1.0 ml/kg of body weight/hour for 30 minutes. If no adverse reactions occur, the rate of administration may be gradually increased (it is recommended to increase by 0.5-1.5 ml/kg of body weight/hour every 10

| Bioven | Page 43 |
|----------------------------|---------------------------------|
| Trial Code: 2021-BV-ITP-BP | Version 1.4 from July 03, 2023, |

min). According to the data from clinical studies the maximum rate of administration is 8.5 ml/kg of body weight/hour.

The study drug is administered only in hospital environment while observing the rules of aseptics. The solution should be of room temperature before use. Cloudy solutions and those containing sediment are not used. For the administration of the drug, it is necessary to use a separate infusion system.

When administering the drug, it is necessary to consider the information specified in the relevant sections of the instructions for medical use: administration details, special safety measures, contraindications, interaction with other medicinal products, etc. Including, but not limited to, measures to control the condition of the coagulation system, hydration levels, renal function, etc.

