6.3 Stage of follow-up and completion

The stage lasts from the last administration of the study drug and for 4 weeks.

The procedures are performed according to the schedule of procedures (Section 6.4, Table 1). If a decrease in platelet count $< 30 \times 109/L$ is detected, an additional blood test with platelet count by Fonio is performed one day after the visit.

Face-to-face or telephone/video visits are made to assess the patient's condition. The patient visits the blood collection point for laboratory testing. The investigator fills in all information about the patient's condition and examination results in the IRF.

| Bioven | |
|----------------------------|-------------|
| Trial Code: 2021-BV-ITP-BP | Version 1.2 |

6.4 Schedule of study procedures in tabular form Table 1. Schedule of study procedures.

| Visits | Visits 1 | Vi | sits 2 (госпіт | алізація) | Visits 3 | PLT control | Visits 4 | PLT control | Visits 5 | PLT control | Visits 6 | PLT contro |
|--|------------------------|-----------|----------------|-----------|-----------|----------------|-----------|----------------|-----------|----------------|-----------|---------------|
| Study stage | Screening ² | IMP admin | . IMP admin | Follow-up | Follow-up | every | Follow-up | every | Follow-up | every | Follow-up | every |
| Day relative to the first administration of the drug/Injection | Day (-14 -1) | Day 0 | Day +1 | Day +2 | Day +7 | day* | Day +14 | day* | Day +21 | day* | Day +28 | day* |
| Signing the Informed Consent Form | • | | | | | | | | | | | |
| Collection of demographics data | • | | | | | | | | | | | |
| Collection of anthropometric data, body weight ³ | • | • | • | | | | | | | | | |
| Collection of medical history ⁴ | • | | | | | | | | | | | |
| Objective physical examination 5 | • | • | • | • | • | | • | | • | | • | |
| Measurement of vital signs 6 | • | • | • | • | • | | • | | • | | • | |
| ECG in 12 leads; | • | | | | | | | | | | | |
| Coombs Direct Test (Antiglobulin Test)* | • | | | • | * | | * | | * | | • | |
| Determination of the level of total Ig G in the blood (g/l) | • | | | • | • | | • | | • | | • | |
| General blood test ⁷ | • | | | • | • | * | • | * | • | * | • | * |
| Biochemical blood test 8 | • | | | | | | | | | | • | |
| Blood test for blood group and Rh factor | • | | | | | | | | | | | |
| Coagulogram (PTI, APTT, fibrinogen) | • | | | | | | | | | | | |
| General urine analysis ⁹ | • | | | | | | | | | | | |

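### A repeat course is allowed up to Day 28, but Visit 6 closes the study, leaving 0-16 days of active AE collection after it on the synopsis window

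*Combined protocol and SAP*

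**What the plan says.** The synopsis, section 6.2 and section 7.4 all permit a second course: "Allowed repeat course at same dosage in period 14-28 days from first infusion, if required". A course is two daily infusions of 0.8-1.0 g/kg.

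On follow-up, the synopsis says "This stage lasts for 4 weeks after the last administration of the drug (possible repeat course is not considered", and under duration of treatment "The total period of stay in the study is 4 weeks". Section 6.3 says "The stage lasts from the last administration of the study drug and for 4 weeks" and makes no exception for a repeat. Section 4.4 says "The stage starts after the last administration of the drug and lasts for 4 weeks".

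The table in 6.4 labels its time axis "Day relative to the first administration of the drug/Injection" and marks drug administration on Day 0 and Day +1 only. The synopsis places the last visit at "6th visit (Day +28 + 1-3 days", which is Day 29-31. Section 6.2 gives Day 30 ± 3 for the same visit, and 6.6 gives Day 28 ± 1-3. Section 6.2 says of it: "This is a face-to-face visit. Completion of the study". Section 9.3 ends AE and SAE registration when the patient's participation ends.

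**The concern.** The frequency and severity of AEs are among the study tasks in section 3, and AE and SAE frequencies are the safety endpoints. A repeat course doubles the cumulative dose, from 1.6-2.0 to 3.2-4.0 g/kg. The calendar does not move with it. A patient treated again late in the window reaches the final visit almost at once, and nothing scheduled afterwards asks about new events.

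The protocol's own risk section makes this concrete. Section 2.4 says aseptic meningitis usually appears within hours to two days of infusion and is more frequent at high doses. After a late repeat, Visit 6 can take place before those two days have passed.

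A site also cannot tell from the text when collection stops. If 6.3 governs, participation and therefore AE registration continue for four weeks after the repeat, but no visit or contact exists to collect the data. If the synopsis governs, registration stops at Visit 6.

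**Working it through.** **Inputs.** A course lasts 2 consecutive days. A repeat may start on Day 14 to Day 28 from the first infusion. Visit 6 windows are Day 29-31 (synopsis), Day 27-33 (6.2), Day 25-31 at its widest (6.6) and nominal Day 28 (6.4 table).

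**Formula.** For a course starting on Day s, the last infusion is on Day L = s + 1. Days observed = Visit 6 day − L.

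**The plan's own figure first.** First course: s = 0, so L = 1. With Visit 6 on Day 29-31, 29 − 1 = 28 and 31 − 1 = 30. The stated 4 weeks is reproduced for the first course.

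**Repeat course, days observed after the last infusion:**

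| Visit 6 window | Start Day 14 (L = 15) | Start Day 21 (L = 22) | Start Day 28 (L = 29) |
|---|---|---|---|
| Synopsis, Day 29-31 | 14 to 16 | 7 to 9 | 0 to 2 |
| 6.2, Day 27-33 | 12 to 18 | 5 to 11 | −2 to 4 |
| 6.6, Day 25-31 | 10 to 16 | 3 to 9 | −4 to 2 |
| 6.4 table, Day 28 | 13 | 6 | −1 |

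A negative value means that Visit 6 would come before the last repeat infusion. As a share of 28 days, the synopsis row is 50-57%, 25-32% and 0-7%. The largest entry anywhere is 33 − 15 = 18 days.

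**Alternative readings.** If the whole repeat course must finish by Day 28, the latest start is Day 27 (L = 28) and the synopsis window gives 1-3 days. If the synopsis window is read as Day 28-31, each minimum falls by one day. Neither changes the picture.

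**Two-day aseptic meningitis window against Visit 6 (synopsis days 29, 30, 31).**
- Start Day 28: the window closes on Day 29 + 2 = 31, so it is still open at Visit 6 on Day 29 or 30, that is 2 of 3 possible days.
- Start Day 27: it closes on Day 28 + 2 = 30, so it is still open on Day 29, that is 1 of 3.

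**Scheduled coverage after a repeat.**
- Visit 5 (Day 18-24) falls 3-9 days after a Day 15 last infusion. It registers AEs and takes a blood count. The synopsis and 6.2 also list biochemistry at Visit 5; the 6.4 table and 6.6 do not.
- Visit 6 registers AEs and takes a blood count, biochemistry and a Coombs test.
- About a day after Visit 6 a platelet check is done, but only if the count was below 30 × 10⁹/L. The 6.4 table shows no AE registration against it.

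**Day needed for 28 days after the repeat.** 15 + 28 = Day 43 for a Day 14 start, and 29 + 28 = Day 57 for a Day 28 start. Relative to Visit 6 this is 43 − 31 = 12 to 57 − 29 = 28 more days.

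**The case against.** The strongest reply is that this is a disclosed choice. The synopsis excludes the repeat in terms and fixes the stay at 4 weeks, so it never promised 4 weeks after a second course. That stands: against the synopsis alone there is a gap, not an error.

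A reader might go further and infer that the protocol contradicts itself throughout. The documents do not support that. Section 4.4 directly follows 4.3, which describes a single course, so its last administration can be read as the second infusion of that course. Section 9.3 also has a phrase tying AE recording to the period of drug use, but beside two statements that registration lasts to the end of participation it is better read as loose wording than as a separate stopping rule. The clear mismatch is 6.3 against the synopsis.

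A reader might also infer that repeat-course patients go unmonitored. They do not. Visits 5 and 6 partly cover early repeats, and patients are checked around each infusion. Section 6.6 keeps patients in hospital for 3 days at Visit 2. If a repeat followed that procedure, a Day 28 start would be observed to Day 30; the protocol does not say that it would, and 7.4 also allows a day hospital. Unscheduled visits (6.6.1), follow-up of known AEs (9.4) and reporting of suspected reactions that reach the investigator (9.10) remain available. What survives is that none of these actively looks for new events after a late repeat.

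Finally, a single contact at 28 days does not match a two-day risk window. That is a fair point, and it is why the remedy includes an earlier contact for late repeats. The 28-day length is borrowed from what the plan gives the first course; no delayed risk in the documents requires it.

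**Conclusion.** The point holds as a gap in active AE collection after late repeat courses, together with a mismatch between the synopsis and 6.3. The 0-2 and 14-16 day figures assume the synopsis window for Visit 6, a repeat counted from its second infusion, and a start allowed on any day from 14 to 28. The ceiling of 18 days holds across every stated window.

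The overall size cannot be given, because the plan does not say how many repeats are expected; it could be anything from 0 to all 40 patients. A reader might infer that the reported AE frequency will be biased or that the efficacy claim is weakened. Neither follows: bias would depend on repeats and event rates that the documents do not give, and the length of safety follow-up does not enter the primary endpoint or the non-inferiority conclusion. This is a modest, inexpensive improvement to the safety data.

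**What to change.** Keep Visit 6 where it is for efficacy. Then:

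1. State consistently in the synopsis, 6.3, 6.4 and 9.3 that for repeat-course patients AE and SAE collection continues to 28 days after the last repeat infusion (Day 43-57), closed by one remote contact.
2. Where Visit 6 falls within two days of the last repeat infusion, add a brief remote contact a few days after that infusion. On the synopsis window this can arise only for starts on Days 26-28 (for example, start Day 26: L = 27 and 29 − 27 = 2; start Day 25: L = 26 and 29 − 26 = 3).
3. In 10.3.4, tabulate AEs and SAEs separately after the first course and after the repeat course, with days observed after each.

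The cost falls on repeat-course patients only: one remote contact each, at most two, so 0 to 40 × 2 = 80 contacts in the extreme case, and 12-28 more days in contact with the site. Beyond that there are a few more AE records to code, one extra table, and a protocol amendment needing approval or notification under section 18. No visit moves and no invasive procedure is added.

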2. JUSTIFICATION OF THE STUDY

2.1 Introduction

Primary immune thrombocytopenia (ITP) is an acquired immune mediated disorder characterized by isolated thrombocytopenia, defined as a peripheral blood platelet count less than 100×10^9 /L, and the absence of any underlying cause. Until recently, the abbreviation ITP stood for idiopathic thrombocytopenic purpura, but due to the current knowledge of the immune mediated mechanism of the disease, and the absence or minimal signs of bleeding in most cases have led to a revision of the terminology.

In Europe, adult ITP has an incidence of 1.6 to 3.9 cases per 100,000 per year with increasing incidence with older age and equal for the sexes except in the mid-adult years (30-60 years), when the disease is more prevalent in women. Childhood ITP has an incidence of between 1.9 and 6.4 per 100,000 per year with equal distribution between the sexes. [1]

ITP is classified by duration into newly diagnosed, persistent (3-12 months' duration) and chronic (≥ 12 months' duration). Whereas ITP in adults typically has an insidious onset with no preceding viral or other illness and it normally follows a chronic course, ITP in children is usually short-lived with at least two-thirds recovering spontaneously within 6 months. [1]

Signs and symptoms vary widely. Many patients have either no symptoms or minimal bruising, whereas others experience serious bleeding, which may include gastrointestinal hemorrhage (GI), extensive skin and mucosal hemorrhage, or intracranial hemorrhage (ICH). The severity of thrombocytopenia correlates to some extent but not completely with the bleeding risk. Additional factors (eg, age, lifestyle factors, concomitant medications, congenital or acquired coagulation disorders) affect the risk and should be evaluated before the appropriate management is determined. Although death from bleeding is a serious problem, it has been reported that the estimated incidence of fatal bleeding ranges from 0.02 to 0.04 cases per adult patient-year risk.

The diagnosis of ITP is an exclusion diagnosis when the history, physical examination, complete blood count, and examination of the peripheral blood smear do not suggest other etiologies for the thrombocytopenia [2]. Physical examination should be normal aside from bleeding manifestations. The isolated thrombocytopenia with normal indicators of red blood cells and white blood cells are defined in the complete blood count. Anemia caused by significant blood loss may be present but it should be proportional to the amount of bleeding and may result in iron deficiency. The normal or big size of platelets may indicate in a peripheral blood smear, in the same time there should be no deviations in morphology of red blood cells and white blood cells. Currently, bone marrow examination is usually not performed in patients with typical manifestations.

The main goal of ITP treatment is to provide a platelet count that can prevent massive bleeding, rather than adjusting the platelet count to normal. Treatment of ITP should be selected individually for each patient and it is rarely indicated in patients with platelet counts above $50 \times 10^9/L$ in the absence of bleeding, trauma, surgery or high-risk factors (persons who receive anticoagulation therapy). The threshold value of the number of platelets required for the diagnosis of ITP is $100 \times 10^9/L$ [2]. In some patients the disease may be asymptomatic, in others - manifested by hemorrhagic syndrome with different severity. It is known that at the level of platelets $30-50 \times 10^9/L$ due to minor trauma excessive ecchymoses occur and at the level of platelets $10-30\times 10^9/L$. [3].

The management of ITP varies widely and current international guidelines recommend several first- and second-line options, including some medicinal products that have not been approved in the EU for this particular condition.

| Bioven | Page 21 |
|----------------------------|---------------------------------|
| Trial Code: 2021-BV-ITP-BP | Version 1.4 from July 03, 2023, |

First line treatment options include corticosteroids, intravenous immunoglobulin (IV Ig) and intravenous anti-D immunoglobulin (the latter only for non-splenectomised Rhesus-D positive patients). Patients who fail to respond or who relapse face the options of treatment with second line drug therapy or splenectomy but there is no clear evidence to support the best approach. Splenectomy can provide long term efficacy in around 60% of cases. Second line drug therapies include high dose corticosteroids, high dose IV Ig or anti-D Ig, vinca alkaloids and danazol, the immunosuppressants cyclophosphamide, azathioprine and cyclosporine or mycophenolate mofetil, and the anti-CD-20 monoclonal antibody [4].

IVIg have been used in the treatment of ITP since 1981, after the publication of P. Imbach et al., Which proved the high effectiveness of IV Ig in the treatment of ITP in children. [5].

The therapeutic effects of IV Ig in ITP include:

- blockade of neonatal Fc receptors on the surface of endothelial cells and acceleration of catabolism of the whole pool of plasma immunoglobulins, including antiplatelet antibodies;
- inhibition of FcγRIIIa- receptors and phagocytosis mediated by them;
- suppression of the expansion of autoreactive lymphocytes by signal transduction through FcγRIIIa;
- idiotype-mediated inhibition of B-cell receptors and neutralization of cytokinessurvival factors: B-cell activation factor (BAFF) and proliferation-promoting ligand (APRIL) [6,7,8]. The binding of anti-idiotypic antibodies (BP) to membrane-bound Ig G or Ig M B-lymphocytes can transmit inhibitory signals and reduce the production of pathogenic auto-BP [9];
- utilization of active components of complement [10].

In addition, IV Ig drugs cause immune tolerance by modulating subpopulations of Tlymphocytes, namely T-reg- increasing their number and changing the quality of the composition [11].

It is likely that the effect of Ig G therapy in time exceeds the half-life of IV Ig [12].

Immunoglobulin drugs for intravenous administration are not generic drugs and cannot not be interchangeable [15,16].

Clinical studies on the efficacy of intravenous immunoglobulin Bioven 10% solution for infusion in immune thrombocytopenia have not been performed.

2.2 Name and description of the investigational drug.

Composition:

active substance: Human normal immunoglobulin for intravenous administration;

1 ml of the drug contains 0.1 g of normal human immunoglobulin;

excipients: glycine (aminoacetic acid), water for injections.

Pharmaceutical form. Solution for infusion.

General physical and chemical properties: transparent or slightly opalescent, colorless liquid or liquid with slightly yellowish color.

Pharmacotherapeutic group. Human normal immunoglobulin for intravenous administration. Code ATC J06B A02.

Pharmacological properties.

Pharmacodynamics properties.

The product is an immunologically active protein fraction (ratio of immunoglobulin G subclasses in the drug product: IgG1: 65.6 %, IgG2: 22.1 %, IgG3: 10.8 %, IgG4: 1.5 %) max. content of immunoglobulin A in the drug product is 50 μ g/ml.

| Bioven | Page 22 |
|----------------------------|--------------------------------|
| Trial Code: 2021-BV-ITP-BP | Version 1.4 from July 03, 2023 |

Active components of the product are antibodies that have a specific activity against different pathogenic agents such as viruses and bacteria including hepatitis A and B, cytomegalovirus, human herpes virus type 1, type 2 and type 6, Epstein-Barr virus, chicken pox, influenza, measles, parotitis, poliomyelitis, German measles, whooping cough, staphylococcus, Escherichia coli, pneumococcus, tetanus and diphtheria toxins. It also has a non-specific activity to increase organism resistance.

The drug product has a low spontaneous anticomplementary activity.

The drug product is a native immunoglobulin G and retains all biological properties: complement activation; effector and opsonocytophagic function.

The product is an immunologically active protein fraction extracted from human blood serum or plasma and screened negative for antibodies to HIV-1, HIV-2, hepatitis C virus and surface antigen of hepatitis B virus, purified and concentrated by use of the fractionation method with wateralcohol precipitating agent that passed the phase of virus inactivation by use of solvent-detergent method and nanofiltration method.

Clinical studies

In an open-label international multicenter phase III study, according to the Guideline on the clinical investigation of human normal immunoglobulin for intravenous administration (IVIg) 28 June 2018 EMA/CHMP/BPWP/94033/2007 rev.3 Committee for Medicinal Products for Human Use (CHMP) the efficacy, safety and some parameters of the pharmacokinetics of Bioven were studied in patients with primary immunodeficiency (PID). Patients received Bioven for 1 year once during every 4 weeks at an average dose of 0.5 g / kg body weight. Patients were evaluated for immunoglobulin levels, the number of cases of infections, clinical and biochemical blood tests. The most important indicators of heart function, respiration, body temperature were determined, and all cases of possible adverse reactions were recorded.

During 1 year of treatment, one case of serious infectious diseases was recorded (2.3%, or 0.023) cases per 1 patient per year). The median minimum concentration of immunoglobulin in blood plasma was significantly higher than the minimum target level of 5 g/l and after 6 months of treatment was 8.6 g/l, and after 1 year - 8.8 g/l.

In the group of 49 patients receiving Bioven, 20 cases of mild (2%) and moderate (0.5%) adverse events were reported, representing a total of 2.5% of episodes of administration. There were no cases of clinically significant abnormalities in laboratory tests that were associated with drug administration or required discontinuation of treatment. In 18 patients (adults and children), Bioven was administered at increasing infusion rates. At the first stage of the study, the rate of administration was increased to 5.0 ml/kg/h (0.08 ml/kg/min); in the second stage - up to 7.0 ml/kg/h (0.11 ml/kg/min). The maximum rate of administration in the third stage was 8.5 ml/kg/h (0.14 ml/kg/min). The incidence of adverse events was low (2 cases per 35 separate injections), they were mild in nature and did not correlate with the infusion rate. Based on the prevalence of side effects and assessment of the dynamics of the main vital signs, the tolerability of Bioven at a maximum rate of 8.5 ml/kg/h (0.14 ml / kg / min) in 94.0% of patients was assessed as good, in 6.0% - as satisfactory.

The clinical efficacy of Bioven in the complex therapy of patients with severe pneumonia caused by coronavirus infection COVID-19 / SARS-CoV-2 is provided by its ability to have an immunomodulatory effect. As a result, the severity of acute respiratory distress syndrome is reduced and, consequently, the degree of respiratory failure is reduced.

The clinical efficacy was confirmed in the clinical study "Open multicenter randomized study of the effectiveness of Bioven, manufactured by Biopharma Plasma, evaluation in the treatment of patients with pneumonia caused by coronavirus infection COVID-19 / SARS-CoV-2" (code research - 2020-BV-BP).

| Bioven | Page 23 |
|----------------------------|---------------------------------|
| Trial Code: 2021-BV-ITP-BP | Version 1.4 from July 03, 2023, |

The study involved 76 patients with a confirmed diagnosis by all criteria. 66 patients who were screened and did not have exclusion criteria were randomized into 2 groups (study group - Bioven + basic therapy and control group - only basic therapy).

Patients were determined by the indicators of the respiratory system, general condition, duration of the need for intensive care, the need for artificial lung ventilation (ALV), the total duration of treatment. Survival during the 28-day follow-up period, laboratory blood counts (general analysis and biochemical), as well as cytokine levels, inflammatory factors and other indicators of the immune system were also assessed.

The results of the study proved the predominant efficiency of the main variable.

Improvement occured significantly faster: in the study group - on day 5 (interquartile range - 3.50-7.25 days), in the control group - on day 9 (interquartile interval - 6.00-14.75 days), p = 0, 0073. The probability of achieving stabilization in patients of the study group was significantly higher by 2.27 times (95% confidence interval (CI) - 1.26-4.11, p = 0.006) than in patients from the control group.

The predominant efficiency is also confirmed by secondary variables. The mortality from COVID-19 was significantly lower, when Bioven was used: 6.25% in the study group (2 cases out of 32 participants), and 23.63% in the control group (8 cases out of 34 participants), p = 0.039.

The duration of lymphopenia was also significantly reduced. The median time to achieve the level of lymphocytes 1000 cells/mm3 and above in the study group was 4 days (interquartile range - 3.00-5.00 days), in the control group - 7 days (interquartile range - 3.00-7.50 days), p = 0.0097. Pharmacokinetics properties.

The high level of efficacy of the Bioven product is provided by a fast and 100% entrance of antibodies into bloodstream as well as by normal elimination half-life.

After intravenous administration the bioavailability of the normal human immunoglobulin in the circulating blood is immediate and complete. It is rapidly distributed between the plasma and extravascular liquid, and the balance between intra- and extravascular compartments is reached in approximately 3-5 days.

For normal human immunoglobulin the half-life is approximately 40 days. This half-life period can differ from patient to patient, especially in case of primary immunodeficiency. IgG and IgG-complexes degrade in reticuloendothelial system cells.

A clinical study of individual pharmacokinetic parameters of Bioven was performed and involved 22 patients. Cmax was 19.94 ± 4.73 g/l, Tmax -0.63 hours, AUC(0-t) -8309.60 ± 2631.49 g/year /l. The content of immunoglobulin in blood plasma was consistently kept above the minimum target level of 5 g/l for at least 28 days after a single administration of Bioven.

Clinical particulars.

Therapeutic indications.

The product should be used for adults, children and adolescents for replacement immunotherapy in the treatment of primary and secondary immunodeficiency and related diseases:

- primary immunodeficiency syndromes: congenital agammaglobulinemia, hypogammaglobulinemia, severe combined immunodeficiency, unclassified variable immunodeficiency, Wiskott — Aldrich syndrome;- secondary antibody deficiency syndrome: cytopenia of different genesis (acute and chronic leukemia, aplastic anemia, situation after cytostatic therapy), severe bacterial and toxic and viral infections (including surgical complications accompanying by bacteremia and septicopyemic conditions and for preparation of surgical patients for operation);

| Bioven | Page 24 |
|----------------------------|---------------------------------|
| Trial Code: 2021-BV-ITP-BP | Version 1.4 from July 03, 2023, |

- autoimmune diseases: idiopathic thrombocytopenic purpura with a high risk of bleeding or prior to surgical intervention to correct platelet level, Guillain—Barre syndrome, chronic inflammatory neuropathy (demyelinating), inflammatory myopathy, Wegener's granulomatosis, dermatomyositis, systemic diseases of connective tissue (rheumatoid arthritis etc.), Kawasaki disease;

- bone marrow transplantation.

Replacement therapy in adults, children, and adolescents (0 - 18 years) in:

- syndromes of primary immunodeficiency (PID) deficiency of antibodies' production;

- secondary immunodeficiency (SID) in patients who suffers from severe or recurrent infections, ineffective antimicrobial treatments and either proven specific antibody failure (PSAF)* or serum IgG level of <4 g / L.

* PSAF= failure to mount at least a 2-fold rise in IgG antibody titre to pneumococcal polysaccharide and polypeptide antigen vaccines.

Use as part of the complex therapy of adult patients with severe pneumonia caused by coronavirus infection COVID-19 / SARS-CoV-2

Study name Clinical study report «Open multicenter randomized study to evaluate the effectiveness of Bioven, manufactured by LLC "Biopharma Plasma", in the complex therapy of patients with pneumonia caused by coronavirus infection COVID-19 / SARS-CoV-2» Year 2020 Clinical center Communal non-commercial enterprise "Kyiv City Clinical Hospital No.17". Department of Anesthesiology and Intensive Care. Communal non-commercial enterprise of Bila Tserkva City Council "Bila Tserkva City Hospital No.3", III Infectious Diseases Department. Communal non-commercial enterprise of Lviv Regional Council "Lviv Regional Clinical Hospital for Infectious Diseases", Department of Resuscitation and Intensive Care Communal non-commercial enterprise "City Clinical Hospital for Infectious Diseases" of Odessa City Council, infectious boxing department No.10. Communal non-commercial enterprise "Kyiv City Clinical Hospital No.4" of the executive body of the Kyiv City Council (Kyiv City State Administration), Department of Anesthesiology and Intensive Care of Infectious Patients. Vinnytsia National Pirogov Memorial Medical University, Department of Infectious Diseases with a course in epidemiology, Vinnytsia National Pirogov Memorial Medical University on the basis of the infectious department of the communal non-commercial enterprise "Vinnytsia City Clinical Hospital No.1". Communal non-commercial enterprise "Ternopil City Municipal Ambulance Hospital", Infectious Diseases Department. Communal non-commercial enterprise "Central City Clinical Hospital of Ivano-Frankivsk City Council", therapeutic department No.1. Communal enterprise "Volyn Regional Clinical Hospital" of the Volyn Regional Council, Department of Pulmonology. Туре Efficacy and safety Identifier 2020-BV-BPDesign and type of Open, multicenter, randomized, controlled, in parallel groups control Investigated drug: -dose; 0.8-1.0 g/kg 1 time per day; for 2 days -regime; -way of administration i.v. drip, 1 ml / min Number of subjects 76 Healthy / diagnoses of Severe pneumonia, according to the criteria (Appendix 10 to the "Standards of medical care "CORONAVIRUS DISEASE (COVID-19)", approved by the Order of the Ministry the patients of Health of Ukraine from 28.03.2020 № 722 "Organization of medical care for patients with coronavirus disease (COVID-19)") Duration of treatment Shortterm (2 days) Finished. Full. Study status and report type General Conclusion: Results 1) The predominant efficacy by the main variable in the inclusion of BIOVEN in the complex scheme of treatment of patients with pneumonia caused by coronavirus infection COVID-19 / SARS-CoV-2 has been proven. The median of achievement of
